Because of the difficulties encountered in producing a specific H5N1 vaccine, and the animal data showing appreciable cross-protection of LAIV with other influenza A viruses, this study will contribute significantly to our understanding of human immune cross-protection to H5N1 following single, dual or prime boost vaccination with currently available seasonal influenza vaccines. The dosing regimes proposed here for healthy adults are designed to achieve the maximal immune response so that the chance of detecting any measurable cross-protection is maximized. Although safety data on dual dosing with influenza vaccine in healthy adults is limited, the available data from children and adults with chronic medical conditions do not suggest there will be significant additional risks from the second dose.

IV.7. Additional Background Information and Justification for Amendment 6

Memory B cells are known to persist for a lifetime and therefore represent an ideal repository for antibody specificities generated by an individual after vaccination (Lanzavecchia, 2009). Unlike plasma cells, memory B cells can be immortalized by Epstein Barr virus (EBV). The EBV-transformed memory B cells produce large amount of antibodies; however the efficiency of B cell immortalization and cloning is low. An improved method of EBV immortalization has now been established using the TLR9 ligand CpG ODN, which is able to enhance the efficiency of EBV B-cell immortalization more than 100-fold (Traggiai, 2004). This method has been employed to dissect the human antibody response to pathogens such as, SARS (Traggiai, 2004), avian influenza H5N1 (Simmons, 2007), HIV (Corti, 2010), and dengue (Beltramello, 2010).

Preliminary analysis of data from WRAIR #1525 indicates that serum from a subset of subjects exhibited potent *in vitro* cross-reactivity to H5N1 and pandemic H1N1 2009. The observed antibodies are probably generated from long-lived, cross-reactive memory B cells produced in response to a prime-boost vaccination with seasonal influenza vaccine, since it is likely that these subjects had never previously been exposed to H5N1 and/or pandemic H1N1 2009.

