We propose to attempt to produce human monoclonal antibodies from the original samples collected from those subjects with high responses to allow for further analysis of the immune response to influenza vaccines. Subjects will be re-contacted to assess willingness to participate in an additional blood sampling under a minimal-risk human use protocol. A greater understanding of cross-reactive memory B cell responses to influenza neuraminidase and hemagglutinin may eventually lead to new/novel preventive and therapeutic strategies.

V. OBJECTIVES

The hypothesis to be tested in this study is that heterologous prime-boost vaccination of healthy adults with a prime boost regimen of trivalent LAIV (FluMist®) and trivalent IIV (Fluzone®) will induce cross-immunity to a variety of H5N1 avian influenza viruses and human influenza viruses.

Therefore the primary objectives of this study are:

- 1. To establish whether a prime boost strategy using seasonal LAIV and IIV can augment cross-reactivity with H5N1 and human influenza strains.
- 2. To detect the presence of antibodies that can inhibit infection with H5N1 and human influenza strains in microneutralization, plaque reduction, or H5 pseudotyped lentiviral particle-based assays after vaccination with seasonal LAIV and IIV.
- 3. To establish the breadth of antibody responses to H5N1 strains and human influenza strains using ELISA, microneutralization, plaque reduction, H5 pseudotyped lentiviral particlebased assays, neuraminidase inhibition assay, and hemagglutination inhibition after vaccination with seasonal LAIV and IIV.
- 4. To observe T-cell responses following vaccination with seasonal LAIV and IIV.
- 5. To attempt to generate human monoclonal antibodies that are cross-reactive to enzyme neuraminidase and hemagglutinin of H5N1 and pandemic H1N1 2009 in order to investigate further the human response to influenza vaccination

Secondary objectives are to describe the adverse event profile of 2 doses of influenza vaccine given approximately 8 weeks apart in healthy adult volunteers.

VI. METHODS

VI.1. Study Endpoints

The primary study endpoints will be determination of pre and post vaccination immune responses in 26 healthy human subjects to 2 doses of seasonal influenza vaccine including whether there is *in vitro* cross-reactivity against H5N1 virus as follows:

- 1. Antibodies ELISA titers calculated as the dilution factor required to give an optical density of 0.5.

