To detect antibodies that inhibit infection of cells with influenza virus, microneutralization assays will be performed using Madin-Darby canine kidney (MDCK) cells. Serum and nasal wash samples will be heat-inactivated (30 min at 56°C) and serial dilutions will be pre-incubated with H5N1 virus or swine flu H1N1 2009 in 96 well plates. After 1-2 h incubation at 37°C in a 5% CO2, 100 μ l of MDCK cells at 1.5 x 105 /ml will be added to each well and the plates will be incubated for 18 hours. MDCK monolayers will be washed with PBS and fixed in cold 80% acetone for 10 min. The presence of viral protein will be detected by ELISA with a monoclonal antibody to the influenza A NP. The second antibody conjugated with peroxidase will be added and incubated for another 1 h. Plates will be washed, and specific enzyme substrate will be added. The reaction will be stopped with 1 N sulfuric acid. The absorbance will be measured at 490 nm. The average A490 will be determined for quadruplicate wells of virus-infected (VC) and –uninfected (CC) control wells, and a neutralizing endpoint will be determined by using a 50% specific signal calculation. The endpoint titer will be expressed as the reciprocal of the highest dilution of

serum with A490 value less than X, where X = [(average A490 of VC wells) - (average A490 of CC wells)]/2 + (average A490 of CC wells). Sera which tested negative at a dilution of 1/20 will be assigned a titer of 10. The assay will be performed in the BSL3 lab, Mahidol University.

VI.10.2.5. Neuraminidase inhibition assay

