In addition there will be an in-house study monitor assigned to this study to ensure compliance with GCP/ICH standards. Monitoring will consist of a pre-study site visit, regular monitoring visits and a post-study visit.

XII. STATISTICAL METHODS

XII.1. Sample Size and Power

This is a descriptive study designed to detect trends in safety and immune responses that would warrant expanded investigations of potentially promising combinations {Lancaster, 2004} {Browne, 1995}. The sample size of 8 subjects in arms 3 and 4 and 5 in arms 1 and 2 is in the range of what is considered adequate for phase I trails and is not based on sample size and power calculations {Stephenson, 2005} {Lin, 2006} {Nicholson, 2001}.

Recruitment of subjects is likely to be affected by the limited number of US citizens resident in Bangkok who fulfill the eligibility criteria. Hence there will be no stratification of enrolment based on gender; this and other possible confounders (such as prior receipt of influenza vaccines) can be addressed in future large-scale trials.

XII.2. Study Outcome Analysis

Primary Analysis

Immunological data and other continuous variables will be expressed as geometric means and standard deviations if the data are normally distributed, and the vaccine groups compared using parametric tests. If not normally distributed they will be expressed as medians and the range and interquartile range given; comparison between groups will then be by non-parametric tests.

Secondary Analyses

In vivo (AE) data will be analyzed as follows: categorical data will be presented using counts and percentages, whilst continuous variables will be presented using the mean, (standard deviation) or median (range and interquartile range), and number of subjects. Percentages will be rounded to a maximum of one decimal place. All statistical tests will be performed using a 5% significance level, leading to 95% confidence intervals. Differences in incidence of reported AEs between doses and vaccines will be determined. Statistical analyses will be carried out in-house using Stata 10.0 (College Station, Texas).

XIII. ETHICAL CONSIDERATIONS

XIII.1. Study Approval

Scientific approval for this study will be obtained from the Scientific Review Committee at AFRIMS. Ethical approval will be sought from the WRAIR IRB (FWA 00000015) and the USAMRMC ORP HRPO. This study will be governed by ICH GCP guidelines.

XIII.2. Risks and Benefits of Participating

Benefits

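### XII.2 summarises a floored H5N1 microneutralization titre only as a continuous variable, although Objective 2 asks about detection; responder counts with exact intervals should be added

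*Protocol*

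**What the plan says.** Protocol V, Objective 2, is worded as a detection question: "To detect the presence of antibodies that can inhibit infection with H5N1 and human influenza strains", by microneutralization, plaque reduction or H5 pseudotype assay.

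Protocol VI.10.2.4 gives the microneutralization titre a floor: "Sera which tested negative at a dilution of 1/20 will be assigned a titer of 10". VI.1 lists that endpoint as a titre, with no rule for a positive result or a rise.

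Protocol XII.2, Primary Analysis, fixes the summary: "Immunological data and other continuous variables will be expressed as geometric means and standard deviations if the data are normally distributed", with parametric comparison of the groups. Otherwise, "If not normally distributed they will be expressed as medians and the range and interquartile range given", with non-parametric comparison. Counts and percentages appear only under Secondary Analyses, for adverse-event data.

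On how many subjects might respond, IV.2.5 says there were no results for antigenically shifted strains, and IV.7 reports that "serum from a subset of subjects exhibited potent" cross-reactivity. Neither gives a rate.

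**The concern.** A titre with many values at one substituted constant is poorly described by a single measure of location. If only a minority of an arm exceeds the first dilution, the median is the constant itself, and an arm with 3 of 8 responders has the same median as an arm with none. IV.7 considers it likely that the cross-reacting subjects had never met H5N1, so many values at the floor are plausible, above all at Day 0. Such data would hardly pass as normal, so the protocol's own rule leads to the median.

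At stake is how clearly the trial can report on Objective 2. The natural result is a number of subjects out of a number tested, with an interval, and XII.2 plans neither. Nor does it plan a per-subject rise, although the Study Summary says that responses will be compared with baseline. The protocol does set positivity rules for M2e staining (VI.1, item 8) and for T-cell staining (VI.10.2.8), but the primary analysis has no proportion in which to report those either.

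**Working it through.** **Inputs**

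- Arm sizes, from XII.1: "The sample size of 8 subjects in arms 3 and 4 and 5 in arms 1 and 2 is in the range of" what is usual for such trials. 5 + 5 + 8 + 8 = 26, which agrees with the stated total. The size "is not based on sample size and power calculations", so there is no power figure to reproduce.
- Floor: titre 10 for sera negative at 1/20 (VI.10.2.4).
- Proportion *p* of subjects with titre 20 or more: **not in the protocol**. It is an assumption, shown over a range, and first taken as equal in all arms.

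**Step 1. When is the median 10?** With n = 5 the median is the third value, so it is 10 when at most 2 subjects exceed the floor. With n = 8 it is the mean of the fourth and fifth values, so it is 10 when at most 3 do.

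**Step 2. How likely is that?** Let A = P(X ≤ 2 | n = 5, p) and B = P(X ≤ 3 | n = 8, p), both binomial. All four medians are 10 with probability A² × B². At p = 0.25, A = 0.237 + 0.396 + 0.264 = 0.896 and B = 0.886, so the product is 0.63.

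| p | n = 5 | n = 8 | all four arms |
|---|---|---|---|
| 0.10 | 0.991 | 0.995 | 0.973 |
| 0.20 | 0.942 | 0.944 | 0.790 |
| 0.25 | 0.896 | 0.886 | 0.631 |
| 0.30 | 0.837 | 0.806 | 0.455 |
| 0.40 | 0.683 | 0.594 | 0.164 |
| 0.50 | 0.500 | 0.363 | 0.033 |

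**Step 3. Unequal rates.** The trial's hypothesis favours the heterologous arms (n = 8 each). With 20% in the arms of 5 and 40% in the arms of 8, all four medians are 10 with probability 0.942² × 0.594² = 0.31.

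**Step 4. What else would be printed?** Take invented titres. For n = 8 with 10 (five times), 40, 80 and 160, the median is 10, the range 10 to 160 and the interquartile range 10 to 50. For n = 5 with 10 (three times), 40 and 80, the median is 10, the maximum 80 and the interquartile range 10 to 40. The response is visible, but the number of responders is not stated.

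**Step 5. What would a count give?**

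- For 3 of 8, the exact (Clopper-Pearson) 95% interval is 8.5% to 75.5%.
- With no responders, the upper limit is 1 − 0.025^(1/n): 52% for 0/5, 37% for 0/8 and 13% for 0/26.
- At p = 0.20, the chance of at least one responder, 1 − 0.80^n, is 0.67 (n = 5), 0.83 (n = 8) and 0.997 (all 26).

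**The case against.** The other side has several good points.

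- **No response rate is given.** IV.7 names no number and no assay, takes H5N1 and pandemic H1N1 2009 together, and speaks of potent reactivity; it does not say that the remaining subjects were below 1/20. This stands, so the probabilities above are conditional.
- **The median is not the only summary.** Any titre of 20 or more shows as a maximum above 10. With 2 of 5 or 3 of 8 responding, the upper quartile also lies above 10 under the usual definitions. This stands. A range and quartiles still give neither the proportion nor an interval.
- **The substituted value does little harm to the comparison.** In the non-parametric branch, any constant below 20 gives the same ranks. The geometric mean is reserved for data judged normal. This stands.
- **Dichotomising loses information.** Comparing 0/5 with 5/8 gives a two-sided Fisher p of (56 + 40 + 1)/1287 = 0.075. This tells against replacing the titres, not against adding a count beside them.
- **A statistical analysis plan, not seen here, may define responders.** True, and silence alone would be no finding. But XII.2 is not silent: it names the primary summary for all immunological data, and that summary fits a detection objective poorly.
- **This is one assay among nine listed endpoints in a descriptive pilot.** This stands, and it limits the weight of the point.

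**Conclusion.** The point holds as a modest mismatch between objective and summary. If about 25% or fewer of the subjects exceed the floor, the median will be 10 in all four arms with probability of about 0.63 or more. At 40% this falls to 0.16 and the problem largely disappears. These figures assume independent subjects and one common rate. Whatever the rate, up to 2 of 5 or 3 of 8 responders leave an arm's median at 10.

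A reader might infer more, which the protocol does not support:

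- That most H5N1 titres are expected at the floor. No rate is stated.
- That Objective 2 cannot be answered. The range and quartiles show whether anyone responded, positives can be counted from the same titres, and plaque reduction and pseudotype assays also serve this objective.
- That the other titre assays share the problem. VI.10.2.3, VI.10.2.6 and VI.10.2.7 give no starting dilution or floor value for hemagglutination inhibition, plaque reduction or the pseudotype assay.

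**What to change.** In XII.2, keep the planned titre summaries and non-parametric comparisons. Add, per arm and visit, the number and percentage of subjects with an H5N1 microneutralization titre of at least 20, and with at least a four-fold rise from Day 0, each with an exact 95% confidence interval. The cut-off of 20 follows from the assay rule. The four-fold criterion is not in the protocol and would have to be stated as a choice; from a Day 0 value of 10 it requires 40 or more, so the two counts can differ. Do the same for the other neutralization and hemagglutination inhibition assays only where a starting-dilution floor applies.

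Two further steps are not advised. Counts should not replace titres as the main summary. A geometric mean that treats floor values as left-censored should not be required: at p = 0.20 an arm has no detected titre with probability 0.80^5 = 0.33 (n = 5) or 0.80^8 = 0.17 (n = 8), and the estimate then cannot be formed.

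The cost is a few sentences and one table from data already planned. The intervals will be wide (3 of 8 gives 9% to 76%), as is to be expected with arms of this size.

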- 6) H5 pseudotyped lentiviral particle-based serological assay titer assessed as the highest sample dilution that produces 50% inhibition of virus control.

7) Influenza specific T-cell cytokine production by influenza-specific T-cells defined as the percentage of cytokine-staining cells at least twice background.

8) Human monoclonal antibody production from peripheral blood memory B cells isolated from selected subjects

Duration of Subject Participation

This study will take up to 12 months from enrollment of the first subject to completion of the *in vivo* portion. Each subject will be followed up for approximately 12 weeks following entry into the study (screening, dosing, follow-up). The total study duration will be 2 years.

A subset of previously enrolled subjects may be invited to participate in an additional phase of the study, which will involve consent for use of stored sample and a possible single blood draw if extra sample is required. No follow-up will be required after the day of blood draw

Safety Data Collected

Subjects will complete a symptom diary for 14 days following each dose of vaccine. Adverse event monitoring will continue throughout the study duration.

TABLE OF CONTENTS

| I. | GENERAL INFORMATION | 9 |
|------|--|------|
| II. | INVESTIGATOR PROTOCOL AGREEMENT PAGE | 11 |
| III. | ABBREVIATIONS | 12 |
| IV. | BACKGROUND INFORMATION | 13 |
| | IV.1.INTRODUCTION | 13 |
| | IV.2. IMMUNOLOGY OF INFLUENZA AND INFLUENZA VACCINES | 13 |
| | IV.2.1. INFLUENZA VIRUS | 13 |
| | IV.2.2. AVIAN INFLUENZA H5N1 | 14 |
| | IV.2.3. IMMUNE RESPONSES TO INFLUENZA VIRUS | 15 |
| | IV.2.4. INFLUENZA VACCINES | 15 |
| | IV.2.5. LIVE ATTENUATED INFLUENZA VACCINES | 16 |
| | IV.2.6. VACCINES AGAINST AVIAN INFLUENZA H5N1 | . 16 |
| | IV.3.FLUMIST® LIVE, ATTENUATED INFLUENZA VACCINE | 18 |
| | IV.3.1. PRODUCT INFORMATION | 18 |
| | IV.3.2. SAFETY AND TOLERABILITY FOLLOWING SINGLE AND DUAL DOSE ADMINISTRATION IN HEALTHY SUBJECTS | 19 |
| | IV.3.3. SAFETY IN SPECIAL GROUPS | 20 |
| | IV.3.4. SECONDARY TRANSMISSION OF VACCINE VIRUS | 21 |
| | IV.4. FLUZONE® INFLUENZA VACCINE | 22 |
| | IV.4.1. PRODUCT INFORMATION | 22 |
| | IV.4.2. SAFETY AND TOLERABILITY FOLLOWING SINGLE AND DUAL DOSE ADMINISTRATION IN HEALTHY SUBJECTS | 22 |
| | IV.4.3. SAFETY IN SPECIAL GROUPS | 23 |
| | IV.5. CONCOMITANT ADMINISTRATION OF FLUMIST® AND FLUZONE® | 23 |
| | IV.6.STUDY JUSTIFICATION | 24 |

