- 2. Hemagglutination inhibition activity defined as the titer required to completely inhibit hemagglutination);
- Microneutralization assay endpoint titer; determined by using 50% specific signal calculation. The endpoint titer will be expressed as the reciprocal of the highest dilution of serum with A490 value less than X, where X = [(average A490 of VC wells) – (average A490 of CC wells)] / 2 + (average A490 of CC wells).
- 4. Neuraminidase inhibition assay titer defined as the highest sample dilution that produces 50% inhibition of virus control.
- 5. Plaque reduction assay titer assessed as the highest sample dilution that will give a reduction of plaque count of 50%.
- 6. H5 pseudotyped lentiviral particle-based serological assay titer assessed as the highest sample dilution that produces 50% inhibition of virus control.
- 7. Influenza specific T-cell cytokine production by influenza-specific T-cells defined as the the percentage of cytokine-staining cells at least twice background.
- 8. Antibody staining against matrix 2 protein (M2e) expressed cell line. The samples considered positive are those in which the staining intensity is at least twice that for the background.
- 9. Human monoclonal antibody production from peripheral blood memory B cells isolated from selected subjects

VI.2. Study Design

This will be a randomized, open-label, pilot feasibility study of four 2-dose vaccine regimens using two commercially available seasonal influenza vaccines. The *in vivo* phase of the study will entail randomization of up to 26 adult volunteers to receive: either 2 doses of LAIV (5 subjects) (Autologous prime boost regimen 1), 2 doses of IIV (5 subjects) (Autologous prime boost regimen 2), one dose of LAIV followed by one dose of IIV (8 subjects) (Heterologous prime boost regimen 1) or one dose of IIV followed by one dose of LAIV (8 subjects) (Heterologous prime boost regimen 2) (Appendix 2). AE data will be collected into a symptom diary for 14 days following each dose of vaccine. Serum and local (nasal) immunological responses will be evaluated 2 and 4 weeks after each dose. A further 8 subjects will be recruited to act as replacements in case of drop-outs.

VI.3. Study Site

The *in vivo* phase of the study will take place at the U.S. Embassy Medical Unit, Bangkok, Thailand. In selected cases individuals may elect to have scheduled follow-up visits (which do not involve vaccination) performed at AFRIMS. Immunology testing will be done at the

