T cell responses will be assessed by intracellular cytokine staining (ICS). Peripheral blood mononuclear cells (PBMC) will be isolated from blood using density gradient centrifugation as described {Thitithanyanont, 2007}. PBMC (10⁶ cells) in 200ul will be cultured in 96 wells plates with stimulatory antigens (peptide pool or viral proteins from H5N1 virus, human seasonal influenza virus, or swine flu H1N1 2009). All peptide-or protein-stimulated PBMC cultures will contain 1 ug/ml of anti-CD28 and 1 ug/ml of anti-CD49. Staphylococcal enterotoxin B and media control will be used as positive and negative controls, respectively. After the initial 2 h of stimulation, Golgiplug will be added to inhibit cytokine secretion. After 18-20 h of incubation, cells will be washed and stained for CD4 and CD8. The stained cells will be washed and treated with fixation/permeabilization solution and then stain with antibodies against IFN-g and IL-2. Isotype-match control antibody will be used to confirm the staining specificity. The stained cells will be analyzed by 4-color FACS. Approximately 200,000 to 400,000 events in the lymphocyte gate will be acquired. The samples considered positive will be those in which the percentage of cytokine-staining cells is at least twice that for the background or in which there is a distinct population of brightly cytokine-positive cells. The CD4 T cell population will be analyzed by excluding CD8 T cells, and vice versa for analysis of the CD8 T cell population. The ICS assay will be conducted at Immunology BSL2 lab, AFRIMS.

VI.10.2.9. Antibody staining against matrix 2 protein (M2e) expressed cell line

HEK 293 stably expressing M2e on the cell surface will be stained with a 1: 10 dilution of sera samples and then detected by florescent dye conjugated anti-human antibodies. Stained cells will be analyzed by flow cytometry.

VI.10.2.10. Monoclonal antibody production

Peripheral blood memory B cells from selected subjects will be isolated using a fluorescence-activated cell sorter in a BSL2 laboratory. These isolated B cells will be immortalized with EBV in the presence of TLR 9 ligand CpG ODN. The resulting antibodies produced by the immortalized B cells will be screened for neutralizing antibodies against neuraminidase and hemagglutinin of H5N1 and pandemic H1N1 2009. Positive cultures will then be cloned by limiting dilution.

VI.11. Stopping Rules

There will be no interim analysis and therefore no stopping rules for this study.

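### T-cell positivity is defined one way in the endpoint list and more loosely in the assay section, and the twice-background ratio has no safeguard when background counts are low

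*Protocol*

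**What the plan says.** Item 7 of the primary endpoints, in both the Study Summary and section VI.1, rests on a single criterion: "percentage of cytokine-staining cells at least twice background".

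Section VI.10.2.8, which describes the intracellular cytokine staining (ICS) assay, accepts a sample as positive on either of two grounds: "at least twice that for the background or in which there is a distinct population of brightly cytokine-positive cells". No frequency, intensity or gating limit says what makes a population distinct or bright.

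The same section fixes the acquisition: "Approximately 200,000 to 400,000 events in the lymphocyte gate will be acquired". Those events are then divided by subset ("The CD4 T cell population will be analyzed by excluding CD8 T cells, and vice versa"), and the cells are stained for two cytokines, IFN-γ and IL-2. On controls it says "Staphylococcal enterotoxin B and media control will be used as positive and negative controls, respectively". The media control is presumably the source of the background value. The number of control wells is not given, and no minimum event count, minimum difference or test against the control is stated.

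**The concern.** There are two separate problems.

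1. **The sections disagree.** The criteria within VI.10.2.8 are alternatives and do not conflict with each other. The conflict is between that section and item 7. The extra route can only add positives, it depends on the reader's eye, and nothing says which section governs a primary endpoint.
2. **A bare ratio ignores counting error.** Antigen-specific cytokine-positive cells can be rare. When the control tube holds only a handful of positive events, a doubling by chance is common. When it holds none, twice background is zero and every sample satisfies the rule as written, even one with no stimulated events.

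At stake is whether a positive ICS call means the same thing throughout the report, and whether it can be told from noise when the background is low.

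**Working it through.** **The two definitions side by side.** Take an illustrative sample with 10 positive events in the media control, 15 in the stimulated well, equal cell numbers, and a visibly bright cluster. The ratio is 15/10 = 1.5. Under item 7 it is negative. Under VI.10.2.8 it may be positive.

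**False-positive rate of the ratio.** The protocol states no error rate for this rule, so there is no figure to reproduce.

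Inputs:
- Lymphocyte-gate events N: 200,000 to 400,000 (VI.10.2.8).
- Share of those events in the subset analysed, f: not in the protocol; assumed 20% to 45%.
- Background frequency p: not in the protocol; varied.
- Expected background events: μ = N × f × p.

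Model under no response: control count B and stimulated count S are independent Poisson(μ), with equal cell numbers. Then

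P(false positive) = Σ_b P(B = b) × P(S ≥ max(2b, 1)).

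The floor of 1 is lenient to the protocol, because when b = 0 the literal rule is met by S = 0 as well.

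| μ | False-positive rate, one readout |
|---|---|
| 2 | 32% |
| 5 | 18% |
| 10 | 8.4% |
| 12 | 6.3% |
| 15 | 4.2% |
| 20 | 2.2% |
| 50 | 0.05% |

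The rate falls below 5% between 12 and 15 expected events.

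**Translation to the planned acquisition.** The smallest μ uses 200,000 × 20% = 40,000 cells. The largest uses 400,000 × 45% = 180,000 cells.

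| Assumed background p | μ, range | False-positive rate, range |
|---|---|---|
| 0.005% | 2 to 9 | 10% to 32% |
| 0.01% | 4 to 18 | 2.8% to 22% |
| 0.02% | 8 to 36 | 0.3% to 11% |
| 0.05% | 20 to 90 | at most 2.2% |
| 0.1% | 40 to 180 | at most 0.2% |

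These are pure counting error. With an assumed additional well-to-well coefficient of variation of 30% (gamma-Poisson simulation), the rate is 16% at μ = 10 and still 6.6% at μ = 100.

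**Effect of adding a count-based criterion.** With equal cell numbers, S given S + B is Binomial(S + B, ½) under no response. Require S ≥ 2B and a one-sided exact p ≤ 0.01. Under the Poisson model the false-positive rate is then 0.06% at μ = 2, 0.3% at 5, 0.5% at 10 and 0.6% at 20. It stays below 1% throughout the range 1 to 50. With no control events the criterion asks for 7 stimulated events (½⁷ = 0.0078). With 5 it asks for 17 rather than 10. With 20 it asks for 40, the same as the ratio alone.

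**The case against.** The strongest reply is that the positivity call carries little weight here. Section XII.2 analyses immunological data as continuous (geometric means or medians, then tests between groups), item 7 itself names a percentage, and XII.1 describes the study as descriptive and unpowered. Sections VI.6 and VI.13 keep laboratory staff blind to allocation, so a subjective call is unlikely to favour an arm. All of this stands, and it limits the damage to the comparison of arms. It does not settle which definition applies, nor make an unthresholded judgement reproducible.

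The size of the counting problem is also open to challenge, since the protocol gives no background frequency. That is correct. Under pure counting error the problem is small once background is around 0.05% or more.

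Three stronger readings are tempting and are not supported:

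- *Existing immunity would be scored as a vaccine response.* Neither the ICS rule nor the M2e staining rule (item 8 of VI.1) mentions Day 0. But these rules classify one sample against its own background. The Study Summary plans comparison of cellular responses with baseline, VI.1 covers responses before and after vaccination, and VI.10.1.3 collects cells at Day 0. How the two are combined may sit in an analysis plan that is not shown.
- *Responder proportions per arm are inflated.* The protocol plans no such proportions.
- *Error compounds over two cytokines and two subsets.* That needs a rule counting any positive readout, and independence between readouts. The protocol states no such rule, and the cytokines are measured in the same wells against the same control.

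**Conclusion.** The inconsistency is certain from the text: item 7 and VI.10.2.8 can classify the same sample differently, and the additional route has no threshold.

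The weakness of the ratio is real but conditional. It matters below roughly 12 to 15 expected background events per readout. With the planned acquisition and a 20% to 45% subset share, that can arise at a background of about 0.02% or lower. Well-to-well variation beyond Poisson would widen that range. These figures assume equal cell numbers in the two wells and a single control well.

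The consequence is for the meaning and reproducibility of ICS positivity calls, not for the planned continuous comparison of arms. The change is worth making because it is cheap.

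**What to change.** Put one rule in the Study Summary (item 7), VI.1 (item 7) and VI.10.2.8:

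- A sample is positive if its percentage is at least twice the media control **and** a count-based criterion against that control is met, for example a one-sided exact test at a fixed level such as 0.01. Other count-based criteria would also serve.
- State what happens when the control has no events.
- Report a distinct bright population descriptively; it should not by itself make a sample positive.
- Fix the rule before the ICS data are scored, with scorers blind to allocation.

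Cost: wording in three places, and fewer samples called positive, including some weak true responses where background counts are low. Section IV.7 mentions preliminary analysis of serum data, so the study was already under way at version 6.0. If any ICS data have been scored, they must be re-scored, and the report should say that the rule was changed and when.
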